**5.4 Exclusion criteria**

1. Subjects with guttate psoriasis, pustular psoriasis, erythrodermic psoriasis or active infection (i.e., an infection associated with fever, swollen lymph nodes, and/or signs of localized inflammation of tissue and/or joints). *Note: allergic or vasomotor rhinitis is not exclusionary.*
2. Any newly diagnosed genetic or congenital condition, uncontrolled or serious disease, or any medical or surgical condition, that may either interfere with the interpretation of the clinical trial results, and/or put the subject at significant risk (according to Investigator's judgment) if he/she participates in the clinical trial.
3. Known or suspected allergies or sensitivities to any components of any of the study drugs (see Investigator's Brochure/Product label).
4. Female who is lactating.
5. Female who intends to conceive a child during the clinical trial.
6. Current participation in any other clinical trial of a drug or device OR participated in a clinical trial of a drug or device within 1 month prior to baseline.

7. The subject has received, applied or taken the following treatments within the specified time frame prior to the Baseline visit:

Topical treatment(s) or Procedures:	
• Corticosteroids or topical immunomodulators	2 weeks
• Tar (on areas to be treated with study drug)	2 weeks
• Vitamin D derivatives	2 weeks
• Vitamin A derivatives	2 weeks
• Intralesional steroid injections	4 weeks
Systemic treatment(s):	
• Homeopathic or herbal preparations	1 weeks
• Calcium containing products	2 weeks
• Immunomodulators and biologics known to affect psoriasis	4 weeks
• Corticosteroids or ACTH analogs	4 weeks
• Phototherapy/PUVA therapy	4 weeks
• Laser therapy	4 weeks

8. The subject or subject's parent /legal guardian is unwilling to refrain from use of prohibited medication during the clinical trial (see Section 5.5.5).
9. The subject is vulnerable (such as deprived from freedom) as defined in Section 1.61 of International Conference on Harmonisation (ICH) Guideline for Good Clinical Practice (GCP).
10. The subject has hypercalcemia (serum albumin-adjusted calcium above the upper normal range) at Screening.
11. The subject has urinary calcium:creatinine ratio above the upper normal range at Screening.
12. The subject has history or signs and symptoms of urolithiasis.
13. Subjects with known or suspected disorders of calcium metabolism.

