For AEs and AESIs, whenever possible, the Investigator is to provide a diagnosis rather than to report individual laboratory abnormalities.

A summary of sample volumes and the number of blood samples is detailed in Section 13.2, Appendix 2.

- Urinalysis:

A semi-quantitative urinalysis will be performed. The following parameters will be evaluated: glucose, ketones, blood, proteins, leukocytes, and nitrites.

- Pharmacodynamic parameters:

Serum (non-fasting): calcium, phosphorus, albumin (in order to calculate the serum albumin-adjusted calcium), PTH

Urine: Calcium and creatinine (in order to calculate urine calcium:creatinine ratio) on 24-hour urine collections, when feasible, or fasting (4 hour) urine samples. Subjects that are toilet-trained should be actively encouraged to complete the 24-hour urine collection. In case of Ca:Cr ratio above the normal range on a urine sample after fasting for 4 hours, the measurements should be repeated on a 24-hour urine collection whenever possible.

- Other Assessments

- 1, 25(OH)2D
- 25(OH)D

- Urine Pregnancy Test

Post menarcheal female subjects of childbearing potential will have a urine pregnancy test performed at all visits. Additional urine pregnancy tests may be performed at the Investigator's discretion.

For pre-menstrual subjects who begin menses after the Screening visit, pregnancy tests will be performed according to the Schedule of Assessments (Table 2) for females of childbearing potential (Baseline, Week 4, Week 12, Week 26/ET, and Week 30). In addition, subjects must adhere to the contraceptive methods as outlined in Inclusion Criteria 7.

The screening visit laboratory values must be available prior to the Baseline visit.

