## 5.2. Urine

- 5.2.a. Weeks 4 and 12: Obtain urine sample for urinalysis and for post menarcheal females, also perform a urine pregnancy test on the urine sample collected.
  - 5.2.b. Weeks 4 and 12: Distribute container and provide instructions for 24-hour urine collection to be started 1 day prior to Week 12 and Week 26/ET visits, respectively. The study site should contact the parent/legal guardian 48 hours prior to the visit to remind them to start the urine collection.
  - 5.2.c. Week 12: For PD urine, get the 24-hour urine collection from subject or collect fasting (4 hour) urine sample when 24-hour collection is not possible.
6. Question the subject and parent/legal guardian about the occurrence of AEs. Non-persuasive open ended questions are to be asked, such as “Have you noticed any change in your health since last visit?”
  7. Question the subject’s parent / legal guardian or subject (according to subject’s maturity level) specifically about symptoms of kidney stones e.g. obvious hematuria or pyuria, or vague abdominal or flank pain/ discomfort, or possible pain radiating to the groin area.
  8. Week 12 only: Perform physical examination and record vital signs
  9. Ask the subject and parent/legal guardian whether there have been any changes to his/her concomitant therapies/procedures (added, removed, or changed) since the previous visit. Document all changes on the Drugs/Therapies form in the eCRF.
  10. Collect the study medication that was dispensed at the previous visit.
  11. Review medication compliance and review dosing calendar for completeness.
  12. Weeks 4 and 12: Dispense study medication to the subject’s parent/legal guardian using the IRT system.
  13. Weeks 4 and 12: Provide Cetaphil® Moisturizing Cream and Cetaphil® Gentle Skin Cleanser or equivalents to the subject’s parent/legal guardian.
  14. Ask the subject’s parent/legal guardian to return the study medication for the next visit even if used or unused.
  15. Schedule an appointment for the Week 26/Early Termination Visit and remind the subject and parent/guardian to bring the completed dosing calendar.

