### 8.1.5 Week 30 Follow-up visit

1. For post menarcheal females, collect a urine sample and perform a urine pregnancy test.
2. Record the % BSA involved by psoriasis (excluding face and scalp) (See section 13.3, Appendix 3).
3. Obtain serum samples for laboratory testing (full panel) for subjects in the PK group. For all other subjects, obtain serum samples for laboratory testing at the Investigator's discretion (all subjects). Obtain urine for urinalysis (all subjects).
4. Obtain serum samples for 1,25(OH)2D, 25(OH)D and serum PD parameters for subjects in the PK group. For all other subjects, obtain serum samples at the Investigator's discretion. Prepare them according to the Central Laboratory manual.
5. Obtain 24-hour urine sample for PD urine for subjects in the PK group and send it to the central lab for analysis. For all other subjects, obtain 24-hour urine sample at the Investigator's discretion and send it to the central lab for analysis.
6. For selected subjects enrolled in the PK analysis: Collect blood sample for PK assessment.
7. Evaluate IGA.
8. Evaluate pruritus.
9. Question the subject's parent/legal guardian or subject (according to subject's maturity level) about the occurrence of Adverse Events. Non-persuasive open ended questions are to be asked, such as "Have you noticed any change in your health since last visit?"
10. Question the subject's parent / legal guardian or subject (according to subject's maturity level) specifically about symptoms of kidney stones e.g. obvious hematuria or pyuria, or vague abdominal or flank pain/ discomfort, or possible pain radiating to the groin area.
11. Ask the subject and parent/legal guardian whether there have been any changes to his/her concomitant therapies/procedures (added, removed, or changed) since the previous visit. Document all changes on the Drugs/Therapies form in the eCRF.
12. After collecting all data from the subject (including laboratory samples results), complete the Exit form of the eCRF.

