##### 9.1.1.2 *Key Safety Endpoints*

- Laboratory: Serum albumin-adjusted calcium, urine calcium : creatinine ratio, phosphorus, and PTH.
- Adverse Events

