7.5 Analysis Visit Definition

All efficacy variables, vital signs, and laboratory data will be summarized by analysis visit.

Analysis visit will be assigned according to the following algorithm to summarize the efficacy data by proper visit window interval. Study day is calculated as visit date minus the date of first application plus 1. Visit during treatment period will be used for analysis visits of Baseline to Week 26 assignment. Week 30 Follow-up will be the post-treatment/follow-up visit.

If multiple measurements are taken in the same interval, the one closest to the target study day will be used for the analysis. If two measurements are taken with equal differences in timing compared with the target date, the nominal visit number (recorded on the CRF page) will be used.

Table 2 Analysis Visit for Efficacy Data Summaries

Analysis Visit	Analysis Visit Number in Derived Dataset	Target Study Day	Visit Window for IGA, Pruritus, % BSA(Study Day)
Screening	-1	-	[< 1]
Baseline	1	1	[<= 1]
Week 4	2	29	[2 – 42]
Week 8	3	57	[43 – 70]
Week 12	4	85	[71 – 112]
Week 20	5	141	[113 – 161]
Week 26	6	183	[162- 196]
Week 26(LOCF)	6.999	-	Last available data during treatment period, including Baseline.
Week 30 Follow-up	7	-	Last available data during Follow-up data.

For efficacy data, screening visit will be assigned to analysis visit of screening as recorded on CRF page. If multiple measurements of screening due to rescreening or other unexpected reasons, the screening visit closest to date of first application will be chosen. If there is missing measurement at Baseline, Screening data will be used to impute the missing baseline data, if necessary, i.e. Baseline will be the last available data prior to first application. Only scheduled visit will be assigned into appropriate analysis visit; unscheduled visit will not be assigned to analysis visit, therefore, not in the summary.

When assigning the analysis visits for vital signs, no visit window will be applied; Nominal eCRF visit will be used as analysis visit for summaries.

When assigning the analysis visits for laboratory data, no visit window will be applied, however, the following rules will be applied:

1. If sample date/time is prior to date/time of first application, the data will be considered as screening visit. If multiple measurements of screening due to rescreening, retest or other unexpected reasons, the data closest to date of first application will be chosen.

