2. Lab data from scheduled visit will be considered first when assigning analysis visit of each scheduled visit. If there is no data from scheduled visit available within the visit window, the last of those corresponding unscheduled visit will be considered for assignment of analysis visits.

3. When assigning Final visit, the lab data from the last post-baseline scheduled visit during treatment period will be considered first. If the last scheduled visit during treatment period have missing lab data due to any reason and there are subsequent unscheduled lab data available, the last of those corresponding unscheduled lab data will be assigned as Final visit. Otherwise, the previous visit lab data will be considered in the same manner.

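### Urine calcium:creatinine may come from a 24-hour or a 4-hour fasting collection at each visit, but the SAP analyses it as one parameter, so a switch of collection type can look like a change on drug, in either direction.

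*Protocol*

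**What the plan says.** Protocol 9.1.1.2 lists the key laboratory endpoints: "Laboratory: Serum albumin-adjusted calcium, urine calcium : creatinine ratio, phosphorus, and PTH". SAP 4.2 repeats the list.

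Protocol 7.2.2 lets the urine ratio be measured "on 24-hour urine collections, when feasible, or fasting (4 hour) urine samples", and toilet-trained children are to be encouraged towards the 24-hour collection. The choice is made again on treatment. At Week 12 (Protocol 8.1.3, item 5.2) sites take the 24-hour collection or "collect fasting (4 hour) urine sample when 24-hour collection is not possible", and 8.1.4 has the same instruction for Week 26/ET. Neither document asks a child to stay on the type used at Screening.

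Protocol 7.2.2 adds that when a 4-hour fasting ratio is above range, "the measurements should be repeated on a 24-hour urine collection whenever possible". Exclusion 11 (Protocol 5.4) bars a child where "The subject has urinary calcium:creatinine ratio above the upper normal range at Screening", and names no collection type.

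SAP 7.3.3 plans, for each laboratory parameter, descriptive statistics by visit, change from Screening and a shift table of Screening versus Final against the reference range. It also plans mean-change and spaghetti plots, and box plots for this ratio. Collection type is not mentioned.

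SAP 7.5 sets the rule for choosing values. Rule 1 covers multiple pre-dose values, including retests: "the data closest to date of first application will be chosen". Rule 2 covers the period after baseline: "Lab data from scheduled visit will be considered first when assigning analysis visit of each scheduled visit". Rule 3 applies the same priority to Final.

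**The concern.** The protocol does not treat the two collections as interchangeable: it requires fasting for one, and asks that high results from it be repeated on the other. A within-child change that crosses types therefore compares unlike quantities. Hypercalciuria and kidney stones are named risks of participation (Protocol 1.3), Screening is the only scheduled pre-treatment urine value (Protocol Table 2), and no comparator arm would show a collection effect for what it is. A type switch could produce a false signal or hide a real rise.

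The retest rules add a second difference between the two ends of the comparison. A high 4-hour value followed by a normal 24-hour repeat can drop out of the analysis at Screening. The same sequence on treatment stays in it as a high value.

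**Working it through.** The plan gives no figure on this point: no difference between collection types, no split of children by type, and no variance for the ratio. The check traces the rules, then sizes the effect under stated assumptions.

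**1. Can one child be measured by different types at the two ends?** Yes. Protocol 7.2.2, 8.1.3 and 8.1.4 leave the choice open at each visit, and SAP 7.3.3 and 7.5 do not use type in selecting or summarising values.

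**2. Effect of switching on change from Screening.** Let r be the 24-hour ratio divided by the 4-hour ratio, and f the net share of children switching. Assumptions: r from 0.7 to 1.5, f = 0.20, no drug effect.

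- One child, 4-hour to 24-hour: r - 1 = 0.7 - 1 = -30%, to 1.5 - 1 = +50%.
- Mean change: f x (r - 1) = 0.20 x (-0.30) = -6%, to 0.20 x 0.50 = +10%.
- One child, 24-hour to 4-hour: 1/r - 1 = 1/1.5 - 1 = -33%, to 1/0.7 - 1 = +43%.

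Switches in opposite directions offset in the mean. They do not offset in individual changes, the standard deviation, the shift table or the spaghetti plots. If r = 1 the effect is zero.

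**3. Effect of switching on new above-range values.** Simulation with no drug effect, log-scale SDs of 0.40 between and 0.35 within children (assumed), and one upper limit set two SDs above the mean on the 4-hour scale. Among children in range at Screening, these are above range later:

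| Children | Above range later |
|---|---|
| Stay on 4-hour | about 1.8% |
| Switch to 24-hour, 24-hour ratio 10% higher | about 2.8% |
| Switch to 24-hour, 24-hour ratio 25% higher | about 4.9% |
| Switch to 24-hour, 24-hour ratio 50% higher | about 9.8% |

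If the 24-hour ratio is lower, the effect reverses.

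**4. The retest rules side by side.** Take a 4-hour value above range and a 24-hour repeat in range.

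- At Screening, rule 1 takes the value nearest first application, so the repeat stands.
- After baseline, rule 2 takes the scheduled value, so the high 4-hour result stands. At Final, rule 3 turns to unscheduled data only if the scheduled value is missing.

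**5. How much the retest rules add to exclusion 11.** Same SDs, no drug effect and no type difference, every high value repeated once, eligibility judged on the value used, upper limit at the 95th or 97.5th percentile. Above range at Final:

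| Rule | 95th | 97.5th |
|---|---|---|
| Repeat at Screening, scheduled value at Final (SAP 7.5) | 4.4% | 2.3% |
| First value at both | 3.7% | 2.0% |
| Repeat at both | 1.1% | 0.4% |

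The asymmetry itself adds 4.4 - 3.7 = 0.7 or 2.3 - 2.0 = 0.3 percentage points. Most of the apparent shift comes from the eligibility cut, which leaves no child above range at Screening. Using the repeat at both ends removes most of it. For scale, Protocol 1.3 reports hypercalciuria in 3% of adults in the 52-week study.

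**The case against.** The strongest reply is that no direction or size can be shown. That stands. The inputs in steps 2, 3 and 5 are assumptions, and the mean depends only on net switching.

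A reader might infer that the retest rules simply bias the Screening-versus-Final shift upward. The documents do not support that without conditions. Exclusion 11 already cuts Screening at the upper limit whatever the retest rule, the direction of any type difference is unknown, and the number of children admitted on a repeat is not given.

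The asymmetry also depends on the 24-hour repeat being used at Screening. Protocol 7.2.2 says its general repeat-testing rule does not apply to screening values, but the sentence on the urine ratio carries no such limit and SAP 7.5 rule 1 foresees Screening retests. The reading is reasonable, though not explicit. The SAP also still describes the 140-subject design and omits the 24-hour-repeat sentence.

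A reader might also cite Week 30, where Protocol 8.1.5 says "Obtain 24-hour urine sample for PD urine for subjects in the PK group". That bears only on the Week 30 by-visit change, because Final is the last value during treatment. Nor does age explain within-child change: type is likely to follow age, but that mixes method with age in by-visit levels only. A child who stays on one type gives a like-for-like change.

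There is some protection. Investigators review out-of-range values, the SAP lists subjects who have them, nothing inferential depends on the endpoint, and keeping a scheduled high value is cautious for safety. The laboratory manual, the eCRF or the separate table list may record type. None of this puts type into the planned change or shift summaries.

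**Conclusion.** The point holds as a gap in the SAP. The plan permits a change of collection type within a child and contains nothing that would separate its effect from a drug effect. That the types are pooled is inferred from the absence of any split; no sentence says so. The effect can run either way. The range of -6% to +10% in mean change is illustrative, and rests on an assumed type ratio of 0.7 to 1.5 and a net 20% switching from 4-hour to 24-hour. The retest rules treat the same sequence of results differently before and after treatment, which adds to the truncation from exclusion 11; under the assumptions in step 5 the addition is 0.3 to 0.7 percentage points. An upward bias regardless of conditions is not established. The analysis is descriptive, so the plan should be amended, but no error rate is at stake.

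**What to change.** Amend SAP 7.3.3 and 7.5:

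- Carry collection type (24-hour or 4-hour fasting) for each urine value in the analysis dataset.
- Keep the all-subject summary and add change-from-Screening and shift summaries for same-type pairs, by type. Restricting the analysis to same-type pairs would drop children from a key safety summary of about 100, so the new tables should stand beside the existing ones.
- List subjects whose type differs between Screening and Final.
- Add a sensitivity shift table that uses the 24-hour repeat, where available, both at Screening and after baseline. It makes the retest rule symmetric but can itself change the type, so read it with the same-type tables.

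The cost is SAP wording, one variable, a few extra outputs and smaller n in the same-type tables. How small cannot be computed, because the documents give no split by type. If type is not already recorded at each visit, it also needs to be captured.

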#### **7.2.2.1 IDMC Case Management**

The management of hypercalcemia and PTH-suppressed cases will remain under the responsibility of the IDMC.

All cases of hypercalcemia, confirmed urolithiasis, out of range PTH levels or decreases in PTH of 30% from the subject's Baseline visit will be communicated immediately to the Principal Investigator, to Clinical Safety Officer (see contact detail in section 7.2.3.2.2), and to the IDMC members as alerts, as appropriate. Galderma will receive recommendations from the IDMC on the management of the subject and on the study outcome.

Subjects with microscopic or macroscopic hematuria will be managed according to Investigator discretion. The IDMC will be notified of cases of hematuria as necessary. Management of subjects with suspected urolithiasis will be handled on a case by case basis. Subjects with suspected urolithiasis should temporarily discontinue study drug. If urolithiasis is not confirmed, the subject may resume treatment with study drug. Subjects with confirmed urolithiasis should permanently discontinue study drug use and complete the Week 26/ET visit.

#### **7.2.3 Adverse Events**

Adverse events (AEs) are to be monitored throughout the course of the clinical trial. All AEs are to be reported on the Adverse Event Form of the eCRF with complete information as required. If AEs occur, the main concern will be the safety of the subjects. At the time of the ICF signature, each subject must be provided with the name and phone number of clinical trial center personnel for reporting AEs and medical emergencies.

The subject's parent / legal guardian or subject (according to subject's maturity level), should be asked specifically about symptoms of kidney stones e.g. obvious hematuria or pyuria, or vague abdominal or flank pain/discomfort, or possible pain radiating to the groin area at each study visit.

### **7.2.3.1 Definitions**

#### **7.2.3.1.1 Adverse events (AE)**

According to ICH E2A, an AE is any untoward medical occurrence in a subject or clinical investigation subject administered a pharmaceutical product and which does not necessarily have a causal relationship with this treatment. An AE can therefore be any unfavorable and unintended sign (including an abnormal laboratory value), symptom, or disease temporally associated with the use of a medicinal (investigational) product, whether or not related to the medicinal (investigational) product.

Thus any new sign, symptom or disease, or any clinically significant worsening of an existing sign, symptom or disease compared to the condition at the first visit (including disease treated), should be considered as an AE. Lack of efficacy is not considered as an AE.

Each new episode of a chronic disease (e.g., hay fever, allergy, etc) should be reported as a new AE.

Notes:

- Any new sign or symptom reported by the subject that appears after accidental or intentional overdose or misuse should also be reported as an AE.
- There should be an attempt to report a diagnosis rather than the signs, symptoms or abnormal laboratory values associated with the report of an AE. However, a diagnosis should be reported only if, in the Investigator's judgment, it is relatively certain. Otherwise, symptoms, signs, or laboratory values should be used to describe the AE.
- Pregnancy is not to be considered as an AE; however, is an important medical event that must be monitored as described in Section [7.2.3.2.4](#).

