
Principal statistical method:
	
No inferential statistics are planned for this study.
 
The Safety Population is defined as comprising all of the subjects who have applied the study drug at least once. All data will be summarized based on the Safety Population.
 
The laboratory parameters at scheduled visits and change from Screening at post-baseline visit(s) will be summarized descriptively by visit. A shift table for lab parameters at Screening versus the Week 26/Early Termination will be provided when appropriate.
 
The categorical variables will be summarized by frequency and percentage for each response category (N, %). The continuous variables will be summarized using means, medians, minimum, maximum, and standard deviations for the data collected at each visit and the changes and percent changes from Baseline at each post-baseline visit when appropriate.
 
Treatment-emergent Adverse Events (TEAEs) will be tabulated in frequency tables by System Organ Class and Preferred Term based on the Medical Dictionary for Regulatory Activities (MedDRA). Additional summary tables will be provided for AEs that are considered serious (SAEs), related to the study drug(s), severe, AESIs, and AEs leading to discontinuation. For a given AE, a subject will be counted once even if he/she has experienced multiple episodes of that particular AE. Subgroup summaries of AEs will be provided based on gender, age group, and race when appropriate.
 
<math>C_t</math> will be submitted, after logarithmic transformation (<math>\ln</math>), to paired comparisons of Baseline and each subsequent time point. Ninety percent confidence intervals of the pairwise differences will be calculated using the Student's t statistic. The limits of the intervals will be back-transformed into exponential to obtain 90% confidence intervals of the ratios of geometric means between time points, on the original scale.
 
PK/PD relationships will be investigated by correlating <math>C_t</math> with appropriate PD parameters, using Spearman coefficient and graphical illustrations.

Sample size:
	
Sample Size Justification:          Approximately 167 subjects will be screened to enroll approximately 100 subjects into the study.

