### 7.2 **Safety assessment**

A safety assessment will be conducted for all subjects at the screening visit (from the Informed consent signature) and every subsequent visit. The safety parameters are AEs, (to be recorded as specified in Section 7.2.3), laboratory safety tests, physical examination, and vital signs.

All abnormal findings at the screening visit identified as clinically significant by the Investigator, will be recorded in the Medical History form. For any clinically significant changes from the screening visit, an AE is to be recorded.

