#### 7.2.3.1.5 *Adverse event reporting period*

The clinical trial period during which AEs must be reported is the period from when the subject signed the Informed Consent Form to the end of the subject's participation.

The Sponsor should be informed if the Investigator becomes aware of any unusual safety information or any safety information that appears to be drug-related involving a subject who has participated in a clinical trial, even after a subject has completed the clinical trial. The Investigator should be diligent in looking for possible latent safety effects that may not appear until a medication has been discontinued.

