### 9.1.5 Safety analysis methods

No inferential statistical analysis is planned for safety endpoints of the study.

The laboratory parameters at scheduled visits and change from Screening at post-baseline visit(s) will be summarized descriptively by treatment and by visit. A shift table for lab parameters at Screening versus Week 26/ET will be provided when appropriate.

Only Treatment-emergent Adverse Events (TEAEs) will be summarized. A TEAE is defined as an AE with an onset date on or after the first application of the study drug.

TEAEs will be tabulated in frequency tables by System Organ Class and Preferred Term based on the Medical Dictionary for Regulatory Activities (MedDRA). Additional summary tables will be provided for TEAEs that are considered serious (SAEs), related to the study drug(s), and severe. TEAEs that are AESIs, as well as TEAEs leading to discontinuation will also be summarized. For a given TEAE, a subject will be counted once even if he/she has experienced multiple episodes of that particular TEAE. Subgroup summaries of TEAEs will be provided based on gender, age group, and race when appropriate.

Prior and concomitant therapies and procedures will be summarized. A prior therapy/procedure is one that ends at or before baseline; and a concomitant therapy/procedure is one starting after the baseline visit.

Extent of study drug exposure and compliance will also be summarized.

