7.3.2 Adverse Events

Adverse events will be coded using the Medical Dictionary for Regulatory Activities (MedDRA) dictionary (version 15.0).

Treatment-emergent adverse events (TEAEs) is defined as an AE with an onset date on or after the first application of the study drug. TEAEs will be tabulated in frequency tables by System Organ Class and Preferred Term for whole study and by period (Day 1 to Day 90, Day 91 to End of Treatment, Follow-up period). Additional summary tables will be provided for TEAEs that are considered serious (SAEs), related to the study drug(s), severe, and possibly related to Calcium Metabolism from predefined SOCs/HLGT . TEAEs of special interested and TEAEs leading to discontinuation will also be summarized. For a given TEAE, a subject will be counted once even if he/she has experienced multiple episodes of that particular TEAE. Subgroup summaries of TEAEs will be provided based on gender, race, and age group (2-5 years, 6-12 years, 13-17 years) when appropriate.

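### TEAEs are selected on onset date alone, and no rule says how an AE already open before first application is recorded when it worsens on drug, so some on-drug worsening may be missing from the summary tables

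*Protocol*

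**What the plan says.** **Collection.** The AE reporting period in Protocol 7.2.3.1.5 "is the period from when the subject signed the Informed Consent Form to the end of the subject's participation". In the Protocol's Schedule of Assessments, Screening is at Day -14 and the Baseline visit has a window of 5 days either way.

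**What counts as an AE.** Protocol 7.2.3.1.1 includes "any clinically significant worsening of an existing sign, symptom or disease compared to the condition at the first visit". Protocol 7.2 uses the same reference point: "For any clinically significant changes from the screening visit, an AE is to be recorded".

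**What counts as treatment-emergent.** Protocol 9.1.5: "A TEAE is defined as an AE with an onset date on or after the first application of the study drug". In SAP 7.3.2 a TEAE likewise "is defined as an AE with an onset date on or after the first application of the study drug". Neither has a clause for worsening.

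**What is tabulated.** Protocol 9.1.5: "Only Treatment-emergent Adverse Events (TEAEs) will be summarized". SAP 7.3.2 starts its list of further tables with "Additional summary tables will be provided for TEAEs that are considered serious (SAEs" and continues with related, severe and calcium-metabolism events. Its summaries of special-interest events and of events leading to discontinuation are also of TEAEs. The Protocol synopsis words the same tables differently: "Additional summary tables will be provided for AEs that are considered serious (SAEs), related to the study drug(s), severe".

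**What is listed.** SAP 9 makes all eCRF data available as subject listings. SAP 9.3 plans separate listings of serious, severe, drug-related, special-interest and discontinuation AEs.

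**The concern.** Between consent and first application a child can develop an AE that is properly recorded with a pre-dose onset. Part of this interval may be a washout: Protocol 5.4, criterion 7, asks for 2 weeks off topical corticosteroids, vitamin D derivatives and vitamin A derivatives before Baseline. If that AE then intensifies on the ointment, the intensification is the safety information of interest, but a rule that looks only at onset date cannot see it.

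The special-interest category shows the problem most clearly. Item 3 of Protocol 7.2.3.1.3 depends on severity (severe irritation, severe pruritus). An event that is mild before dosing and severe on drug acquires special-interest status only on drug, yet its onset date can keep it out of the special-interest TEAE summary. Such events are not remote for this product: Protocol 1.3 reports psoriasis in 4% and pruritus in 3% of adults in the 52-week open-label study.

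Safety is the primary objective and there is no control arm, so the AE tables carry much of the evidence. An omission of this kind can only lower the counts.

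**Working it through.** The plan states no figure on this point, so there is none to reproduce. The check applies the written rule to event histories and then gives an illustrative size.

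**1. Length of the pre-dose window.** 14 days + 5 days = up to about 19 days.

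**2. The rule applied.** A TEAE requires onset day ≥ 1, where Day 1 is first application (SAP 7.5).

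- A. Present at Screening, first worsens on Day 30, onset entered as Day 30: 30 ≥ 1, counted.
- B. New on Day -7, severe or serious on Day 30, kept as one record: -7 < 1, not counted.
- C. The same event as B, with a second record opened on Day 30: counted through the second record.
- D. New on Day 30: counted.

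Only B is lost. B and C are the same clinical event and differ only in how the site filled in the form.

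**3. Do the documents decide between B and C?** Protocol 7.2.3.2.1 lists the fields to be entered, including onset date, severity, relationship and outcome. Protocol 7.2.3.1.6 asks for the single most appropriate grade. Protocol 7.2.3.2.2 and 7.2.3.2.3 have the site follow the progress of the same event and send an updated form. The only rule for opening a new record (7.2.3.1.1) covers new episodes of a chronic disease. Together these make B the natural reading, but none of them forbids C.

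**4. Role of the first-visit reference.** An event absent at Screening, mild on Day -7 and severe on Day 30 is worse on Day 30 than at the first visit. It therefore meets the AE definition again on Day 30. The reference point permits C and does not produce B. The loss comes from the onset-only TEAE rule combined with silence on recording.

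**5. Illustrative size, on assumptions only.** Planned enrolment is 100 (Protocol 3). Assume that 10 to 20% of children have an AE starting before first application, that 30 to 50% of these are ongoing at Day 1, and that 10 to 30% of those worsen on drug:

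- low: 100 × 0.10 × 0.30 × 0.10 = 0.3 children
- high: 100 × 0.20 × 0.50 × 0.30 = 3.0 children

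The chance of at least one such child is 1 − (1 − p)^100:

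- p = 0.5%: expected 0.5, chance 39%
- p = 1%: expected 1, chance 63%
- p = 2%: expected 2, chance 87%
- p = 5%, above the range just derived: expected 5, chance 99%

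These figures are for worsening of any grade, with every such event kept as one record. Events that become severe or serious are a fraction of them, and the documents give no basis for that fraction.

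**6. With the definition extended.** History B is counted as one record, because its severity increased on Day 30.

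**The case against.** The strongest case against is that little is lost. Psoriasis is present at Screening by eligibility (IGA 2 or 3) and pruritus is scored there, so either one first worsening on drug is history A and is captured. Irritation caused by the ointment cannot begin before the first application. Washouts longer than 2 weeks lead to screen failure and re-screening, which limits washout inside the study. Worsening of IGA and pruritus is also summarised as efficacy data, laboratory parameters are summarised whatever their AE status, and reasons for discontinuation are tabulated separately. Serious and special-interest events go to the safety officer within 24 hours. All of this stands. It makes the affected group small and keeps the events on record, but it does not put them into the AE tables.

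Three stronger readings are tempting, and the documents do not support them.

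- A reader might infer that such an event can appear in no AE summary table. That holds only if the site keeps one record, which no text requires. The synopsis also words the serious, severe, special-interest and discontinuation tables as AEs. That wording conflicts with 9.1.5, so it neither settles the matter nor can be ignored.
- A reader might blame the first-visit reference for worsening. As step 4 of the working shows, it is not the cause.
- A reader might illustrate the harm with one omitted serious case: the one-sided 95% exact upper limit is 4.66% for 1/100 and 2.95% for 0/100. The arithmetic is correct, but the assumed rates describe worsening of any grade and do not show that one omitted serious case is to be expected. The plan also calls for no inferential analysis of safety.

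**Conclusion.** The point holds as a gap in definition and recording. Both documents select TEAEs on onset date alone, AEs are collected for up to about 19 days before first application, and nothing states how on-drug worsening of an already open AE is entered. An event of this kind that becomes severe, serious or of special interest on drug is left out of the TEAE-based tables if it stays one record and is included if a second is opened. The count therefore depends on site practice, and any error is downward.

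The loss is from summary counts and not from the trial record. Its size cannot be derived from the documents. Under the assumptions in the working it is 0.3 to 3 of 100 children for any worsening, and fewer for severe or serious events. The change is worth making because safety is the primary objective, there is no comparator, and the correction is cheap.

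**What to change.** 1. In Protocol 9.1.5 and SAP 7.3.2, define a TEAE as an AE with onset on or after first application, or an AE with earlier onset that increases in severity or becomes serious on or after first application.
2. State one convention for recording such worsening so that the definition can be applied, for example by keeping the single record and entering the date of worsening. With the wider definition there is no need to require a second record as well; asking for both would invite duplicates.
3. Reconcile the synopsis, which words the serious, severe, special-interest and discontinuation tables as AEs, with 9.1.5, which restricts summaries to TEAEs.

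The cost is a sentence in each document, a line in the eCRF completion guidance and a synopsis edit, all before database lock. TEAE counts may rise slightly.
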